4.4.2 Supportive secondary endpoint(s)

Mean changes for continuous outcomes for other measures of glycemic control and variability:

- Proportion (%) of participants achieving total CV <36% at week 16. To calculate the proportion of participants achieving CV <36%, a sum of the number of participants with CV <36% divided by the total number of participants. The endpoint will be calculated using all CGM glucose readings available throughout each day for two weeks (week 14-16). As this is a binary outcome the endpoint will be summarized with proportions and 95% CI using the Clopper-Pearson exact method. A two-sided 95% CI will be presented.
- Change (%) from baseline (run-in) to week 16 in TIR [70-180 mg/dL] for specific time blocks [12 am – 6 am, 6 am – 12 pm, 12 pm – 6 pm, 6 pm - 12 am, and 6 am – 12 am]. The end point will find the percentage of time spent in the glycemic target range. This is calculated as 100 times the number of recorded measurements in the glycemic target range, (70-180 mg/dL) inclusive, divided by the total number of recorded measurements per time block and comparing the corresponding time blocks from week 16 to baseline in a 14-day period to determine change. Two-sided 95% CIs will be presented.
- The proportion (%) of participants achieving Glucose Management Indicator [GMI] <7% and <9% at week 16. The GMI (%) formula used is $3.31 + 0.02392 * (\text{mean glucose in mg/dL from CGM data})$ (Bergenstal et al., 2018); this step is followed by determining the

number of participants achieving <7% and <9% at week 16. The endpoint will be calculated using all CGM data available throughout each day of the two-week period (week 14-16) for derivation of mean glucose. A two-sided 95% CI will be presented.

- Change from baseline (run-in) to week 16 in the 4-hour PPG area under the concentration time curve from 0 to 4 hours (AUC_{0-4h}) after start of the breakfast meal, including determination of the time to reach maximum associated concentration (T_{max}), are both based on MMTT data. T_{max} will be calculated by finding the time that corresponds to the maximum glucose concentration from $t=0$ over the 4 hrs. The 4 hour PPG AUC will be calculated from the glucose values measured at time 0 (just before the meal), 0.5 hours, 1.0 hours, 1.5 hours, 2.0 hours, 2.5 hours, 3.0 hours, and 4.0 hours post-meal utilizing the “trapezoidal rule” $AUC = \sum_{i=0}^{4 \text{ hr}} \frac{[C_{gluc(i+1)} + C_{gluc(i)}]}{2} (t_{i+1} - t_i)$ where C=concentration, i = specified time intervals in the MMTT, and t =time. Differences in (AUC_{0-4h}) from baseline (run-in) to week 16 will be reported as well as the corresponding T_{max} at baseline and week 16. Two-sided 95% CIs will be presented. This analysis will be based on participants in the enrolled set who have non-missing outcomes at baseline and week 16.
- Proportion (%) of participants at week 16 who spend < 15 minutes/day at a glucose level <54 mg/dL. The endpoint will be summarized based upon CGM data reporting both percentages and 95% CI using the Clopper Pearson exact method. A two-sided 95% CI will be presented.

Measures of glycemic control and variability will be presented at baseline and at the end of the treatment period (Week 16). The mean (SD) and associated 95% CI, as well as minimum, median, and maximum values will be provided.

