8.7 Statistical Analysis Methodology

Statistical analysis will be performed using SAS Enterprise software Version 7.1 or higher. In general, descriptive statistics of quantitative efficacy and safety parameters (result and change from baseline) by scheduled visits will be provided on observed cases (OC; ie, inclusion of only participants having non-missing assessments at a specific visit). The baseline value is defined as the last available value before the first injection of Soliqua 100/33. All efficacy analyses (primary, key secondary, secondary, and other efficacy endpoints) will be performed on the efficacy analysis set. Analysis of demographics, baseline characteristics, and prior and concomitant medications will be provided in detail in the SAP. The extent of study treatment exposure and adherence will be assessed and summarized with dose frequency and duration of treatment.

Continuous data will be summarized using number of observations available, mean, SD, minimum, median, and maximum. Categorical data will be summarized using count and percentage.

Details of the statistical analyses, methods, and data conventions are described in the SAP.

All statistical tests will be 2-sided and performed using a 0.05 significance level, leading to 95% (2-sided) confidence intervals (CIs).

Laboratory values below the lower limit of quantification (LLOQ) will be set to ½LLOQ.

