8.7.3.3 Handling of Missing Data

Missing data will be handled differently in accordance with the reasons for the missing data for both primary and key secondary endpoints. If the missing data are due to technical issues with the CGM device (ie, CGM data are not evaluable if at least 10 out of 14 days [not necessarily consecutive] have <80% of evaluable CGM data per 24-hour period during the run-in period as well as the end of the treatment period [ie, from Weeks 14

to 16]), the participant will be excluded from the analysis (missing completely at random [MCAR] approach). For other reasons for missing measurements (eg, lost to follow-up, discontinued treatment), the Week 16 assessment will be imputed with the baseline value carried forward (missing not at random [MNAR], conservative approach). The assumption that data are MCAR will be evaluated using an association test (eg, Chi-square test for categorical covariates and Pearson correlation coefficient or two-sample t-test for continuous covariates) between baseline covariates and missing data status (ie., participants who have missing data for primary endpoint versus those who have complete data). The reasons for missing the primary endpoint at Week 16 (eg, lost to follow-up, discontinued treatment) will also be presented.

Multiple Comparisons and Multiplicity

A hierarchical testing procedure will be performed. Key secondary endpoints will be evaluated with a one-sample t-test to determine whether there is any change at Week 16 over baseline in succession in accordance with the hierarchy and as long as the endpoints continue to show statistical significance. If one test is nonsignificant (p > 0.05), then the testing will be stopped (or consider all further tests to be only secondary, and no formal conclusions can be drawn).

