4.4 SECONDARY ENDPOINT(S) ANALYSIS

4.4.1 Key/Confirmatory secondary endpoint(s)

4.4.1.1 Definition of endpoint(s)

Key Secondary Endpoints:

- Change (%) from baseline (run-in) to week 16 in glucose total CV. The data for this endpoint come from the CGM data using the glucose readings. The endpoint will be calculated globally (percent change from the total two weeks baseline CV to the two weeks end of treatment week 16 CV). The CV formula used is $CV\%_{total} = \frac{SD_{total}}{\bar{x}} * 100\%$ where $SD_{total} = \sqrt{\frac{\sum(x_i - \bar{x})^2}{n-1}}$, x_i is the individual glucose reading value, \bar{x} is the 14-day mean and n is the number of data points and the % change will be reported. The alternative hypothesis to be tested is that the CV differs between baseline and week 16. A two-sided 95% CI will be presented.
- Change (mg/dL) from baseline (run-in) to week 16 in mean daily blood glucose. These data come from the CGM data and will be calculated for each day by using the average blood glucose for week 16 compared to the parallel day during the run-in period (baseline) [for example, Day 1 of baseline's average blood glucose will be compared to Day 1 of week 16's average blood]. A global average will be computed to determine the average of the mean daily blood glucose for the 14 days at baseline and also at week 16. The global average will be used for hierarchical testing and the mg/dL change will be reported. The alternative hypotheses to be tested is that mean daily blood glucose differs between baseline and week 16. Two-sided 95% CIs will be presented.
- Change (mg/dL) from baseline (run-in) to week 16 in the maximum PPG exposure in the 4 hours after the breakfast meal during the mixed-meal tolerance test collected from the CRF. The analysis is focused on the 4-hour interval at both baseline (run-in) and week 16 from t=0 (the timepoint at which glucose measurement is taken immediately preceding meal administration) throughout the subsequent 4 hours. For each participant, the overall maximum glucose value (mg/dL) within the described 4-hour period will be determined, and the difference between the maximum glucose value at baseline(run-in) and week 16 will be reported. The alternative hypothesis to be tested is that the maximum PPG differ between baseline and week 16. A two-sided 95% CI will be presented. This analysis will be based on participants in the enrolled set who have non-missing outcomes at baseline.

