4.4.1.2 Main analytical approach

The key secondary estimand will be estimated based on the efficacy analysis set using measurements obtained during the study, regardless of intercurrent events. All four endpoints are continuous and will be summarized using the number of observations available, mean, SD, minimum, median, and maximum. Mean changes for continuous outcomes will be presented at baseline and at the end of the treatment period (Week 16). Mean (SD) and associated 95% CI, as well as minimum, median, and maximum values will be provided, and the analysis will be tested with 2-sided tests at 5% significance level.

Key Secondary endpoints will undergo hierarchical testing in the order displayed in [Section 4.6](#), using two-sample t-test. The results of the test will be displayed in a summary table.

Missing data handling of key CGM secondary endpoints will follow the same approach as the primary estimand.

Regarding participants who discontinue treatment early, but complete the early termination visit per protocol and have MMTT collected at the EOT visit, their data will be used if collected on study day 56 or later; otherwise, the week 16 outcome will be imputed. If the week 16 MMTT data were collected prior to day 56 or missed, then the week 16 outcome will be imputed using baseline observation carried forward (BOCF).

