- Change in diabetes medication treatment-related impact and satisfaction, as measured by the DM-SAT, from baseline (run-in) to week 16. The four DM-SAT subscales/domains provide a means for the researcher or clinician to understand which component(s) of diabetes treatment were most responsive to an intervention, distinguish one treatment approach from another, or determine which were appraised more positively or negatively by a patient. DM-SAT questionnaire is comprised of 16-item measurements within 4 subscales/domains: well-being; medical control; lifestyle; convenience
 - Well-being – physical symptoms, mood, and energy.
 - Medical control – how well the medication(s) keep a participant’s blood sugar where the participant thinks it should be, how often are “highs” avoided in a blood sugar test

according to the participant, and how much the participant feels in control of their diabetes.

- Lifestyle - how easy it is for a participant to have a lifestyle they prefer with the diabetes medication they are taking, how much a participant has to plan their social life around their diabetes medication(s), how much a participant plans their physical activity around their diabetes medication(s), how much a participant has to plan their mealtimes because of their diabetes medication(s), and how much time they spend each day on their diabetes medication.
- Convenience - how often are “lows” avoided in a blood sugar test according to the participant, the convenience of their diabetes medication(s) when they are traveling or away from home for more than one day, the way they take their diabetes medication(s), the time(s) of day they must take their diabetes medication(s), and the overall convenience of their diabetes medication(s).

The expectation is that the satisfaction scores will increase from baseline to week 16. Two-sided 95% CIs will be presented. These analyses will be based on participants in the enrolled set who have non-missing outcomes at baseline and week 16.

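### Peak glucose and AUC0-4h/Tmax come from the same meal test but follow different missing-data rules, so they will describe different participants

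*SAP*

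**What the plan says.** **Maximum PPG (key secondary).** SAP 4.4.1.1 requires only a baseline value: "This analysis will be based on participants in the enrolled set who have non-missing outcomes at baseline". For participants who stop early and have an MMTT at the end-of-treatment visit, SAP 4.4.1.2 says "their data will be used if collected on study day 56 or later". If the test was earlier than that or was missed, the Week 16 value is set to baseline, so the change is 0.

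**AUC0-4h and Tmax (supportive secondary).** SAP 4.4.2 requires both tests: "This analysis will be based on participants in the enrolled set who have non-missing outcomes at baseline and week 16". It has no day-56 provision and no imputation.

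**HbA1c and DM-SAT.** SAP 4.5.1 also requires both values on the enrolled set. For DM-SAT the wording is "These analyses will be based on participants in the enrolled set who have non-missing outcomes at baseline and week 16".

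**Windows.** SAP 5.4.5 applies visit windows to post-baseline MMTT, patient-reported and laboratory data. Table 8 gives days 2-60 for Week 8, 61-102 for Week 14 and 103-116 for Week 16.

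**Protocol.** On the analysis set, section 8.7 says "All efficacy analyses (primary, key secondary, secondary, and other efficacy endpoints) will be performed on the efficacy analysis set", and section 8.7.7 repeats the efficacy set for DM-SAT. On missing data, section 8.7.3.3 limits its rule to the first two tiers: "Missing data will be handled differently in accordance with the reasons for the missing data for both primary and key secondary endpoints". Section 8.7 gives observed cases as the general basis for descriptive statistics by visit. SAP 5.2 reports no changes to the planned analyses, and SAP Table 9 does not list a change of analysis set.

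**The concern.** The peak, the area and the time of the peak are three summaries of one glucose curve. A reader will expect them to refer to the same people. As written, a discontinuer with a baseline test contributes to the peak, either through a late early-termination test or as a zero change, and contributes nothing to the area or Tmax. No reason is given.

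The protocol asks discontinuers to complete the last-dosing-day procedures where possible, and it provides for collecting CGM data and then the MMTT (sections 4.4.1.1 and 6.2.2; Schedule of Events, note a). Some of these tests would be collected and then left out of AUC0-4h and Tmax.

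In a single-arm trial the change from baseline is the whole efficacy result. Gastrointestinal events are an identified risk (Protocol 1.3), so those who stop early may well differ from those who finish. The choice of who is counted therefore moves the reported estimate.

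**Working it through.** **1. The plan's own figures.** SAP section 2 assumes a 10-point rise in TIR, SD 25, two-sided 0.05 and 95% power. By the normal approximation, n = (25 × (1.960 + 1.645) / 10)² = 81.2, so 82, as stated. Allowing for 15% dropout, 82 / 0.85 = 96.5, so 97, against the stated 100. The documents give no figure for completers-only against BOCF; the rest is derived here.

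**2. The two rules side by side**

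| Discontinuer's MMTT | Maximum PPG | AUC0-4h, Tmax |
|---|---|---|
| None after baseline | change = 0 | excluded |
| Before day 56 | change = 0 | excluded (Week 8 window) |
| Days 56-60 | observed value used | excluded (Week 8 window) |
| Days 61-102 | observed value used | excluded (Week 14 window) |
| Days 103-116 | observed value used | included |

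If 15 of 100 had no test in the Week 16 window and all had a baseline test, maximum PPG would be reported on 100 and AUC0-4h on 85.

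**3. Completers-only against pure BOCF.** Let m be the mean change among those with both tests and d the fraction without a Week 16 value. BOCF adds zeros, so its mean is (1 − d) × m, and the ratio of the completers-only mean to the BOCF mean is 1 / (1 − d).

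- d = 5%: 1 / 0.95 = 1.053
- d = 10%: 1 / 0.90 = 1.111
- d = 15% (planned dropout): 1 / 0.85 = 1.176

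**4. Completers-only against the actual maximum-PPG rule.** Let f be the share of those d participants who have an early-termination test from day 56, and g their mean change as a multiple of m. The mean becomes m × [(1 − d) + d × f × g], and the ratio is 1 / [(1 − d) + d × f × g]. The documents give neither f nor g, so a range is shown for d = 15%.

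| f | g | Ratio |
|---|---|---|
| 0 | any | 1 / 0.85 = 1.176 |
| 0.5 | 0.5 | 1 / 0.8875 = 1.127 |
| 0.5 | 1 | 1 / 0.925 = 1.081 |
| 1 | 0.5 | 1 / 0.925 = 1.081 |
| 1 | 1 | 1 / 1 = 1.000 |

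At 15% missing, about 18% is the upper limit, provided that early tests from day 56 do not on average show worsening (g not below 0).

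**5. Analysis set.** The efficacy set is the enrolled set restricted to those with at least one dose and compliant baseline CGM (SAP Table 4). The protocol puts AUC0-4h, Tmax, HbA1c and DM-SAT on the efficacy set; the SAP puts all four on the enrolled set. For maximum PPG the SAP disagrees with itself: Table 3 names the enrolled set in one column and the efficacy set in another, 4.4.1.1 says enrolled, and 4.4.1.2 says efficacy.

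**The case against.** **The gap is not fixed by the rule.** A reader might infer that these changes are 18-22% larger simply because of how the SAP is written. The documents do not support that. The 22% end needs 18% missing (100 / 82 = 1.22), but the 82 are participants evaluable for the CGM-based primary endpoint, and a sensor failure does not remove a meal test, an HbA1c or a questionnaire. The 18% end needs every missing participant to be set to zero, whereas maximum PPG keeps early tests from day 56. This objection stands, and the size is stated accordingly.

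**HbA1c and DM-SAT follow the protocol on missing data.** A reader might also infer that completers-only analysis of these two breaches the protocol. It does not. BOCF was planned only for primary and key secondary endpoints, with observed cases as the general descriptive rule. A BOCF version of either would be an addition. This stands in full.

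**The window reading is an inference.** The day-56 sentence speaks of MMTT data without naming maximum PPG, and Table 8 alone would also misplace an early peak value. This stands in part. The sentence sits under the key secondary endpoints, where maximum PPG is the only meal-test outcome, and 4.4.2 has nothing like it. Read literally, AUC0-4h loses the test. If the sponsor meant otherwise, the SAP should say so.

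**The analysis-set change is probably small.** The SAP treats baseline CGM non-compliance as a screen failure (Schedule of Events, note r), so the two sets should nearly coincide, and no favourable bias from the wider set has been shown. That limits its effect but does not explain why it is undeclared.

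**BOCF is not the truth.** It is one conservative single imputation, so the observed-case mean cannot be called wrong by reference to it. This stands. The case for change rests on consistency within one test and on using data already collected.

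**Conclusion.** The point holds as a cheap improvement. The SAP applies two missing-data rules to one meal test without giving a reason. The peak and the area of the same curve will be reported on different participants, and early-termination tests from days 56-102 will be used for one and, read literally, dropped for the other.

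At the planned 15% dropout the completers-only mean change is up to about 18% larger than a BOCF mean, falling to 8-13% if half of the missing participants have a usable test from day 56 with half to all of the completers' effect, and to zero if all do with the full effect. This assumes that dropout equals missing meal tests and that the early tests do not on average show worsening. The actual missing fraction is unknown from these documents.

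For HbA1c and DM-SAT the missing-data handling is consistent with the protocol. What remains, for these and for AUC0-4h and Tmax, is the unlisted move from the efficacy set to the enrolled set. All four lie outside the testing hierarchy in SAP 4.6, so primary and key secondary conclusions do not change.

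**What to change.** - In SAP 4.4.2, analyse AUC0-4h and Tmax on the same participants as maximum PPG, with the same day-56 rule and missing-data rule, and show the observed-case result beside it.
- In SAP 5.4.5, state that the day-56 rule overrides the Table 8 window for every outcome taken from the meal test.
- Settle one analysis set for the meal-test outcomes (including the maximum-PPG row of SAP Table 3), HbA1c and DM-SAT. Either use the protocol's efficacy set, or keep the enrolled set and list the change in SAP 5.2 and Table 9 with its reason.
- A BOCF row for HbA1c and DM-SAT is optional, as a sensitivity result only.

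The cost is a few sentences in the SAP, a few extra table rows, and a somewhat less favourable AUC0-4h change if discontinuers benefited less. No new data are needed.

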4.5 TERTIARY/EXPLORATORY ENDPOINT(S) ANALYSIS

4.5.1 Definition of endpoint(s)

Mean changes for continuous outcomes for additional measures of glycemic control and variability in participants with T2DM:

- Change (mg/dL) from baseline (run-in) to week 16 in mean of daily difference [MODD] of glucose levels. Using the formula: $\frac{\sum_{t=0}^{t=95} |[Day_{j+1,t} - Day_{j,t}]|}{\text{number of paired timepoints}}$ where t =time period in the 24 hour day by 15 minute intervals and j = day to calculate MODD for each participant 13 times comparing Day 2 to Day 1, up to Day 14 to Day 13 for Baseline and for week 16. The average absolute daily differences at each 15-minute interval of CGM data will be summarized using descriptive statistics. Two-sided 95% CI will be presented.
- Change (%) from baseline (run-in) to week 16 in TAR >250 mg/dL. The percentage of time spent above the glycemic target range will be calculated as 100 times the number of the total number of 15-minute increments of CGM data where a participant’s blood glucose falls above normal range (>250 mg/dL) in a 14-day period divided by the total number of 15-minute increments read (1344 number of 15-minute increments). This will

be calculated for baseline and for week 16 to report the difference. A two-sided 95% CI will be presented.

- Change (%) from baseline (run-in) to week 16 in TBR <70 mg/dL. The percentage of time spent below the glycemic target range will be calculated as 100 times the number of the total number of 15-minute increments from CGM data where a participant's blood glucose falls below normal range (<70 mg/dL) in a 14-day period divided by the total number of 15-minute increments read (1344 number of 15-minute increments). This will be calculated for baseline and for week 16 to report the difference. A two-sided 95% CI will be presented.
- Correlation of change in percentage of TIR [70 – 180 mg/dL] and change in PRO from baseline (run-in) to week 16. Analysis will be done between each of the 4 domains (well-being, medical control, lifestyle, and convenience), PRO overall, and change in TIR. The purpose of finding the correlation of change from baseline to week 16 for percentage of TIR and PRO is to determine the relationship between those two continuous variables.
- Correlation of percentage of TIR [70 – 180 mg/dL] and HbA1c percentage achieved at week 16. The correlation of percentage of TIR and HbA1c achieved at week 16 will estimate the relationship between the two variables.
- Association of participants reaching 60 units/day insulin glargine U100 and TIR > 70%.
- Change in HbA1c percentage from baseline (run-in) to week 16. The alternative hypothesis to be tested is that the HbA1c will decrease from baseline to week 16. A two-sided 95% CI will be presented. This analysis will be based on participants in the enrolled set who have non-missing outcomes at baseline and week 16.
- Change in the percentage from baseline (run-in) to week 16 for TITR (70-140 mg/dL). The end point will determine the percentage of time spent in the glycemic tight target range. This is calculated as 100 times the number of recorded measurements in the glycemic target range, (70-140 mg/dL) inclusive, divided by the total number of recorded measurements per time block and comparing week 16 to baseline over a 14-day period to determine change. A two-sided 95% CI will be presented.
- Proportion (%) of participants with TIR (70–180 mg/dL) > 70% each day at week 16. To calculate the proportion of participants achieving TIR of >70% each day, a sum of the number of participants with more than 67 15-minute intervals with glucose values in range per day for all compliant days divided by the total number of participants. The endpoint will be calculated using all CGM glucose readings available throughout each day for two weeks at the end of study. As this is a binary outcome the endpoint will be summarized with proportions and 95% CI using the Clopper Pearson exact method. A two-sided 95% CI will be presented.
- Proportion (%) of participants with $\geq 5\%$ absolute improvement from baseline in TIR (70-180 mg/dL). Absolute improvement is defined as an increase in TIR from baseline to week 16. To calculate the proportion of participants achieving $\geq 5\%$ in TIR absolute improvement from baseline a sum of the number of participants with a positive percent change $\geq 5\%$ will be divided by the total number of participants. The endpoint will be calculated using all CGM glucose readings available throughout each day for each two-

week time blocks. As this is a binary outcome the endpoint will be summarized with proportions and 95% CI using the Clopper Pearson exact method. A two-sided 95% CI will be presented.

- Proportion (%) of participants with $\geq 10\%$ absolute improvement from baseline in TIR (70-180 mg/dL). Absolute improvement is defined as an increase in TIR from baseline to week 16. To calculate the proportion of participants achieving $\geq 10\%$ absolute improvement in TIR from baseline a sum of the number of participants with a positive percent change $\geq 10\%$ are divided by the total number of participants. The endpoint will be calculated using all CGM glucose readings available throughout each day for each two-week time blocks. As this is a binary outcome the endpoint will be summarized with proportions and 95% CI using the Clopper Pearson exact method. A two-sided 95% CI will be presented.
- Proportion (%) of participants with improvement in HbA1c $>0.5\%$ points without an increase in TBR (<54 mg/dL) of $>0.5\%$. Improvement is defined as an increase in HbA1c from baseline to week 16. To calculate the proportion of participants achieving $>0.5\%$ improvement of HbA1c from baseline and with $< 0.5\%$ change in TBR participants will be summed then divided by the total number of participants. The endpoint will be summarized based upon CGM data reporting both percentages and 95% CI using the Clopper Pearson exact method. A two-sided 95% CI will be presented.
- Proportion of participants with $\geq 10\%$ absolute improvement from baseline in TIR (70-180 mg/dL) without an increase in TBR (<54 mg/dL) of $>0.5\%$. Absolute improvement is defined as an increase in TIR from baseline to week 16. A sum of participants with both $\geq 10\%$ of improvement from baseline in TIR and no increase in TBR of more than 0.5% will be divided by the total number of participants. The endpoint will be summarized based upon CGM data reporting both percentages and 95% CI using the Clopper Pearson exact method. A two-sided 95% CI will be presented.
- Proportion of participants with TIR (70–180 mg/dL) $>70\%$ and TBR (<70 mg/dL) $<4\%$ at Week 16. To calculate the proportion of participants achieving TIR $>70\%$ and TBR $<4\%$, a sum of the number of participants with both TIR $>70\%$ and TBR $<4\%$ divided by the total number of participants. The endpoint will be summarized based upon CGM data reporting both percentages and 95% CI using the Clopper Pearson exact method. A two-sided 95% CI will be presented.
- Change in diabetes medication treatment-related impact and satisfaction, as measured by the DM-SAT, from baseline (run-in) to week 16. The four DM-SAT subscales/domains provide a means for the researcher or clinician to understand which component(s) of diabetes treatment were most responsive to an intervention, distinguish one treatment approach from another, or determine which were appraised more positively or negatively by a patient. DM-SAT questionnaire is comprised of 16-item measurements within 4 subscales/domains: well-being; medical control; lifestyle; convenience
 - Well-being – physical symptoms, mood, and energy.
 - Medical control – how well the medication(s) keep a participant’s blood sugar where the participant thinks it should be, how often are “highs” avoided in a blood sugar test

according to the participant, and how much the participant feels in control of their diabetes.

- Lifestyle - how easy it is for a participant to have a lifestyle they prefer with the diabetes medication they are taking, how much a participant has to plan their social life around their diabetes medication(s), how much a participant plans their physical activity around their diabetes medication(s), how much a participant has to plan their mealtimes because of their diabetes medication(s), and how much time they spend each day on their diabetes medication.
- Convenience - how often are “lows” avoided in a blood sugar test according to the participant, the convenience of their diabetes medication(s) when they are traveling or away from home for more than one day, the way they take their diabetes medication(s), the time(s) of day they must take their diabetes medication(s), and the overall convenience of their diabetes medication(s).

The expectation is that the satisfaction scores will increase from baseline to week 16. Two-sided 95% CIs will be presented. These analyses will be based on participants in the enrolled set who have non-missing outcomes at baseline and week 16.

